3.6 Trial Duration

The maximum duration of an individual subject's participation in the trial conduct is approximately 1 year.

Approved

4 TRIAL TEST ARTICLES

The investigational product (IP) under evaluation in this trial is Quad-NIV alone or adjuvanted with Matrix-M1 adjuvant. Discussions on the IP are presented in this section.

4.1 Overview of Product and Manufacturing Process for Clinical Trial Material

Novavax's Quad-NIV is manufactured in the same manner as Tri-NIV, based on purified, recombinant full-length HA that self-assembles into distinct nanoparticle structures of approximately 20 to 40 nm [Smith 2017]. The baculovirus/*Spodoptera frugiperda* (SF9) insect cell system is used to clone and express recombinant influenza HAs from the influenza strains recommended for the 2018 - 19 Northern Hemisphere influenza season: A/Michigan/45/2015 (H1N1); A/Singapore/INFIMH-16-0019/2016 (H3N2); B/Colorado/06/2017 (Victoria lineage); and B/Phuket/3073/2013 (Yamagata lineage) [VRBPAC 2018, WHO 2018].

Matrix-M1 is a saponin-based adjuvant, which is co-administered with an antigen to induce an enhanced immune response. Matrix-M1 is manufactured by mixing defined, partially-purified extracts of the bark of the *Quillaja saponaria* Molina tree, termed Fraction-A and Fraction-C, with cholesterol and phosphatidylcholine in the presence of a detergent.

4.2 Manufacture of Bulk Antigen

4.2.1 Recombinant Baculovirus

The recombinant influenza HA genes are cloned into *E. coli* flashBAC GOLD baculovirus transfer vectors (Oxford Expression Technologies, Oxford, UK). The HA genes are under the transcriptional control of the baculovirus AcMNPV polyhedrin promoter at the 5' end and includes a poly (A) sequence at the 3' end. For each influenza strain, recombinant baculovirus expressing a HA gene are identified, plaque-purified, and amplified for use in the manufacture of recombinant influenza HA antigens.

4.2.2 Production and Purification of Quad-NIV

Manufacture of each HA protein antigen is initiated by infecting SF9 cells in exponential growth with baculovirus containing the strain-specific HA gene. After infection, cells are collected by centrifugation, washed with a detergent-free buffer, and then lysed in the presence of detergent to release membrane-bound HA protein. Leupeptin hemi-sulfate salt is added to the lysis buffer to protect the HA protein from cellular proteases released during the lysis step. The supernatant containing the HA protein is separated from cell debris through the use of depth filtration before it is purified on an ion exchanger trimethylaminoethyl (TMAE) column. The B/strain requires an additional chromatography step following TMAE to further remove host cell proteins. The B/strain flow-through fraction is loaded onto a Capto Blue mixed-mode chromatography to capture and remove additional baculovirus and SF9 host cell proteins, while B/strain HA is recovered in the flow-through fraction. Nanofiltration is then performed to remove viruses from the HA product stream of both A and B strains. The HA protein is then loaded onto a lentil lectin column, which selectively binds the glycosylated protein. After washing, the HA protein is eluted from the column with buffer containing methyl- α -D-mannopyranoside (MMP) and

Approved

polysorbate 80 (PS80). Eluted fractions are processed by tangential flow filtration, to concentrate the HA product and exchange it into the final formulation buffer. The product is then diluted to a final formulation containing sodium phosphate and PS80, and then filtered (0.22 µm) to produce bulk drug substance that is clear and colorless, and contains no preservatives. Each HA bulk drug substance is stored at $\leq -60^{\circ}\text{C}$ until the 4 strains are mixed and diluted to the target concentration with buffer, and filled as drug product. The final composition of the drug product formulation is 25 mM sodium phosphate, 150 mM sodium chloride, 100 mM arginine hydrochloride, 5% w/v trehalose, and 0.03% PS80, pH 7.5.

4.2.3 Manufacture of Matrix-M1 Adjuvant

Matrix-M1 is manufactured by mixing defined, partially-purified extracts of the bark of the *Quillaja saponaria* Molina tree, termed Fraction-A and Fraction-C, with cholesterol and phosphatidylcholine in the presence of a detergent. Detergent removal by diafiltration results in the formation of stable cage-like structures of 2 types, designated Matrix-A and Matrix-C, based on the precise *Quillaja* fraction incorporated. The designation, Matrix-M, refers generically to a blend of Matrix-A and Matrix-C particles together at any ratio. An 85:15 ratio (by weight) of Matrix-A and Matrix-C particles, respectively, yields Matrix-M1. For a more detailed description of the manufacturing process of Matrix-M1 adjuvant, refer to the current Matrix-M Adjuvant Safety Data Supplement.

4.3 Description of Clinical Trial Dosage Formulation

The HA protein content in each purified bulk influenza antigen drug substance is measured and the 4 HA drug substances are mixed and diluted to the target concentration specified in the trial protocol in 25 mM sodium phosphate, 150 mM sodium chloride, 100 mM arginine hydrochloride, 5% w/v trehalose, and 0.03% PS80, pH 7.5. The formulated drug product for Quad-NIV is then filled into 2R single-use glass vials; with or without admixture with Matrix-M1 as appropriate.

Matrix-M1 adjuvant is formulated in phosphate buffer, 150 mM sodium chloride, pH 7.2, and filled into 2.0 mL single-use glass vials.

Quad-NIV drug product co-formulated with Matrix-M1 adjuvant is filled directly into vials at appropriate concentrations. The buffer composition is the same as bulk antigen concentration alone, ie, 25 mM sodium phosphate, 150 mM sodium chloride, 100 mM arginine hydrochloride, 5% w/v trehalose, and 0.03% PS80, pH 7.5. The co-formulated drug product will be filled into 2R single-use glass vials.

For drug products requiring mixing, the Pharmacy Manual will provide detailed instructions for the unblinded pharmacist.

4.4 Fluzone HD – Active Comparator

Fluzone® High-Dose (Sanofi Pasteur) will be administered based on manufacturer's instructions, which will be provided in the Pharmacy Manual.

Approved

Nanoparticle Influenza Vaccine, Quadrivalent
Novavax, Inc. Confidential
Version 3.0 – 21 August 2018

qNIV-E-201 Protocol
Page 47

4.5 Flublok Quadrivalent – Active Comparator

Flublok Quadrivalent® (Sanofi Pasteur, previously Protein Sciences) will be administered based on manufacturer's instructions, which will be provided in the Pharmacy Manual.

4.6 Placebo

Sterile isotonic saline for injection will be used as placebo for recipients in Groups A, B, C, D, F, and G at their Day 28 injection (supplied in single-dose glass vial at a concentration of 9 mg/mL sodium chloride manufactured by Fresenius Kabi).

4.7 Investigational Product Packaging, Storage, and Handling

All IPs (ie, Quad-NIV alone, Matrix-M1 adjuvant alone, Quad-NIV co-formulated with Matrix-M1 adjuvant) will be packaged in validated shipping containers for distribution to the investigational sites under refrigerated conditions. The Quad-NIV and Matrix-M1 vials and cartons will be labeled with the following information: manufacturer's name and address, product name, manufacture date, storage requirements (2 - 8°C), directions for use, and any other investigational product labeling appropriate to the jurisdiction in which the trial is conducted. Fluzone HD, Flublok Quadrivalent, and placebo will be packaged, shipped, and stored based on manufacturer's instructions. All IP and comparator materials should be stored at 2 - 8°C in a temperature-monitored refrigerator. Access to this refrigerator should be limited to designated site personnel.

4.8 Compliance and Drug Accountability

All quantities of the test articles must be reconciled at the completion of enrollment and a written explanation provided for any discrepancies. Unless specific written instructions to the contrary are provided by Novavax, all unused test articles are to be inventoried, and either destroyed or returned to Novavax (or designee) by the clinical site upon notice by Novavax or the site monitor. All used vials will be accounted for on the clinical site's IP Dispensation Log and verified prior to destruction.

Approved

5 SELECTION OF TRIAL SUBJECTS

5.1 Inclusion Criteria

Subjects must meet all of the following criteria to be eligible to participate:

- 1) Clinically-stable adult male or female, ≥ 65 years of age. Subjects may have 1 or more chronic medical diagnoses, but should be clinically stable as assessed by:
 - Absence of changes in medical therapy within 1 month due to treatment failure or toxicity,
 - Absence of medical events qualifying as serious adverse events within 2 months; and
 - Absence of known, current, and life-limiting diagnoses which render survival to completion of the protocol unlikely in the opinion of the investigator.
- 2) Willing and able to give informed consent prior to trial enrollment, and
- 3) Living in the community and able to attend trial visits, comply with trial requirements, and provide timely, reliable, and complete reports of adverse events.

5.2 Exclusion Criteria

Subjects will be excluded if they meet any of the following criteria:

- 1) Participation in research involving investigational product (drug / biologic / device) within 45 days before planned date of first injection.
- 2) Participation in any previous Novavax's influenza vaccine clinical trial(s).
- 3) History of a serious reaction to prior influenza vaccination, known allergy to constituents of Fluzone HD, Flublok Quadrivalent, or polysorbate 80.
- 4) History of Guillain-Barré Syndrome (GBS) within 6 weeks following a previous influenza vaccine.
- 5) Received any vaccine in the 4 weeks preceding the trial vaccination and any influenza vaccine within 6 months preceding the trial vaccination.
- 6) Any known or suspected immunosuppressive illness, congenital or acquired, based on medical history and/or physical examination.
- 7) Chronic administration (defined as more than 14 continuous days) of immunosuppressants or other immune-modifying drugs within 6 months prior to the administration of the trial vaccine. An immunosuppressant dose of glucocorticoid will be defined as a systemic dose ≥ 10 mg of prednisone per day or equivalent. The use of topical, inhaled, and nasal glucocorticoids will be permitted.
- 8) Administration of immunoglobulins and/or any blood products within the 3 months preceding the administration of the trial vaccine or during the trial.

Approved

Nanoparticle Influenza Vaccine, Quadrivalent
Novavax, Inc. Confidential
Version 3.0 – 21 August 2018

qNIV-E-201 Protocol
Page 49

- 9) Acute disease at the time of enrollment (defined as the presence of a moderate or severe illness with or without fever, or an oral temperature $\geq 38.0^{\circ}\text{C}$, on the planned day of vaccine administration).
- 10) Any condition that in the opinion of the investigator would pose a health risk to the subject if enrolled or could interfere with evaluation of the vaccine or interpretation of trial results (including neurologic or psychiatric conditions deemed likely to impair the quality of safety reporting).
- 11) Known disturbance of coagulation.
- 12) Suspicion or recent history (within 1 year of planned vaccination) of alcohol or other substance abuse.

Approved

6 TRIAL ASSESSMENTS AND PROCEDURES

A trial schematic flowchart is provided in [Appendix 1](#). A detailed description of procedures performed at each visit is provided in Section [6.1](#).

6.1 Trial Visit Procedures

6.1.1 Day 0 – Screening Visit

The following procedures will be performed on the day of the planned vaccination:

- Written informed consent will be obtained in conformance with Section [11.3](#) of this protocol.
- Inclusion and exclusion criteria review consistent with Section [5](#).
- Review of medical history, including influenza vaccination history in the previous 3 years (with emphasis on 2017 - 18 vaccine) and history of adverse reactions to prior influenza vaccines and allergies.
- Medication history, including concomitant medications and vaccines within the last year.
- Physical examination including the head, eyes, ears, nose, and throat (HEENT), abdomen, extremities, and at least inguinal, cervical, and axillary nodes, gross motor function, and skin; vital signs (heart rate, blood pressure, respiratory rate, and oral temperature), height, and weight.

Note that further procedures may be performed at the investigator's discretion in order to adequately screen subjects against eligibility criteria and/or to confirm medical history. Potential subjects who meet all of the inclusion criteria and none of the exclusion criteria may be enrolled. *Note: Subjects should be free of acute illness (defined as the presence of a moderate or severe illness with or without fever, or an oral temperature $\geq 38.0^{\circ}\text{C}$) in order to receive the test article injection. Subjects presenting with an acute illness on Day 0 may return to the trial site within the next 7 days to receive their injection provided symptoms have resolved; no repetition of baseline serology or clinical laboratory testing is necessary if the subject returns within 7 days.*

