6.1.2 Day 0 – Injection 1 Visit

All subjects with confirmed eligibility will have the following procedures performed:

- Randomization to a treatment group.
- Blood draw for baseline immunogenicity testing (20 mL, see Section [7.2](#)) and clinical safety assessments (10 mL).
- Approximately 189 subjects from 3 preselected sites (or 63 subjects per site; to target a minimum 20 evaluable subjects per treatment group) will provide additional blood samples (27 mL) at 2 time points (ie, Days 0 and 7) to support testing of cell-mediated immune responses (CMI). Consent documentation at these sites will be suitably modified. Note: For logistical reasons, these subjects will be drawn entirely from those enrolled in Stage 3 of the trial.

Approved

- Alcohol swab cleansing of the injection site followed by IM injection of the assigned trial treatment into the deltoid muscle of the non-dominant arm. *Note: If the non-dominant arm is not available for the injection due to post-surgical changes, skin changes, or prior injury, the dominant arm may be used.*
- Monitoring for any AEs for approximately 30 - 60 minutes following vaccination.
- Post-injection vital sign collection (heart rate, blood pressure, respiratory rate, and oral temperature) at 30 - 60 minutes following vaccination.
- Distribution of the subject diary, thermometer, and a measuring tool to facilitate documentation of any AEs (solicited and unsolicited), concomitant medications, physicians visits, or hospitalizations, occurring from the time of discharge from the trial clinic on Day 0 through Day 6 (inclusive). Subjects will also be instructed to call the trial clinic for any grade 3 (severe) solicited or unsolicited health events, and/or health status changes of concern to the subject.
- Schedule the Day 3 telephone contact and the Day 7 visit before subjects may be dismissed from the clinic.

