8.1.4 Clinical Laboratory Findings as AEs

Clinical laboratory parameters will be tabulated in trial reports by grades using the TGS provided in the **Trial Operations Manual**, which is based on the FDA Guidance for Industry, Toxicity Grading Scale for Healthy Adult and Adolescent Volunteers Enrolled in Preventive Vaccine Clinical Trials (September 2007). Minor adaptations may be made to the grade ranges for some parameters to conform with the normal, high, and low reference ranges established at the central laboratory selected for the trial.

Laboratory values that show an increase in the toxicity grade relative to baseline values in the same subject, and *attain* at least Grade 2 (eg, normal or Grade 1 to Grade 2 or higher) will be reported as AEs. Repeat testing will be conducted as defined below until the laboratory parameter returns to baseline, becomes stable, or an explanatory diagnosis is available:

- Grade 2 events - weekly, from the time the investigator becomes aware of the abnormal laboratory parameter.
- Grade 3 events - every 72 hours, from the time the investigator becomes aware of the abnormal laboratory parameter.

The investigator may also elect to report less severe abnormalities as AEs, at his/her discretion, if the abnormality is of sufficient concern to trigger, or should have triggered, a diagnostic evaluation (including repeat testing).

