## 12.1 Baseline Definitions

For all analyses, baseline will be defined as the last non-missing measurement prior to the first administration of the study material. For immunogenicity analysis, baseline will be the sample drawn prior to the first vaccination, on the day of vaccination.

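### For a subject deferred for acute illness, safety blood from the ill day can stand as the laboratory baseline and keep a Day 28 Grade 2–3 value from being a mandatory adverse event

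*Protocol*

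**What the plan says.** **The waiver.** Protocol 6.1.1 states: "Subjects presenting with an acute illness on Day 0 may return to the trial site within the next 7 days to receive their injection". The illness must have cleared by then. The note adds that "no repetition of baseline serology or clinical laboratory testing is necessary if the subject returns within 7 days". The synopsis screening note carries the same waiver. Acute illness here means a moderate or severe illness, or an oral temperature of at least 38.0°C.

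**The order of procedures.** Protocol 6.1.1 lists consent, eligibility review, history, examination and vital signs, but no blood draw. The safety draw (10 mL) is in 6.1.2, which opens "All subjects with confirmed eligibility will have the following procedures performed". Exclusion 9 in Protocol 5.2 excludes a subject with acute disease on the planned vaccination day.

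**The baseline.** SAP 12.1 says that for all analyses "baseline will be defined as the last non-missing measurement prior to the first administration of the study material". It then adds a stricter rule for one class of data: "For immunogenicity analysis, baseline will be the sample drawn prior to the first vaccination, on the day of vaccination". The safety laboratory has no such rule.

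**What depends on the baseline.** Protocol 8.1.4 requires AE reporting for "Laboratory values that show an increase in the toxicity grade relative to baseline values in the same subject" that also reach "at least Grade 2 (eg, normal or Grade 1 to Grade 2 or higher) will be reported as AEs". Protocol 10.4.1.1 summarises mean change from baseline and change in toxicity grade at Day 28. Protocol 7.1 schedules safety laboratory samples on Days 0 and 28 only.

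**The concern.** The waiver has meaning only if safety blood was taken while the subject was ill. A value disturbed by illness is a poor reference for what vaccination does. It can raise the threshold that a Day 28 value must pass to become a mandatory AE, and it distorts the change summaries. Adverse laboratory changes are a named part of the primary safety endpoint (Protocol 3.2.1). With one scheduled post-vaccination sample, no later scheduled measurement would show that the baseline was wrong.

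There is also a plain inconsistency. The waiver presupposes a sample that Protocol 5.2 and 6.1.2, read in order, would not allow on the ill day. Sites could follow either reading, and nothing in the documents flags the subjects concerned.

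**Working it through.** The plan gives no figure to reproduce. The check is a reading of the rules, an enumeration of the AE rule, and a look at what a count would need.

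**1. Which sample is the baseline?** Take a subject bled on the ill day and injected up to 7 days later.
- If the sample is not repeated, the ill-day value is the last non-missing one before dosing, so SAP 12.1 makes it the baseline.
- If it is repeated before injection, the repeat replaces it under the same sentence.

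**2. The AE rule.** A Day 28 value is a mandatory AE when its grade is above the baseline grade and is at least 2. I assume laboratory grades 0 to 3, which fits the 1, 2 or 3 grade changes in Protocol 10.4.1.1; the scale itself is in the Trial Operations Manual. That gives 4 baseline grades × 2 Day 28 grades = 8 combinations.

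| Baseline grade | Day 28 Grade 2 | Day 28 Grade 3 |
|---|---|---|
| 0 | mandatory AE | mandatory AE |
| 1 | mandatory AE | mandatory AE |
| 2 | not mandatory | mandatory AE |
| 3 | not mandatory | not mandatory |

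Five combinations are mandatory AEs and three are not (2 to 2, 3 to 2, 3 to 3). Had the baseline been taken after recovery at Grade 0 or 1, all three would have been mandatory. An ill-day Grade 1 value masks no AE.

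**3. The grade-change summary.** If the recovered grade would have been 0:
- ill-day 2, Day 28 2: shown as 0 instead of 2
- ill-day 3, Day 28 3: shown as 0 instead of 3
- ill-day 3, Day 28 2: shown as a fall of 1 instead of a rise of 2
- ill-day 1, Day 28 2: shown as 1 instead of 2 (still an AE)

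**4. The mean-change summary.** Let δ be the ill-day value minus the recovered value. The subject's change is Day 28 minus baseline, so it is off by −δ. If a fraction f of an arm has such a baseline with the same δ, the arm mean is off by −f × δ. A value raised by illness makes the change too low; a lowered value makes it too high. Whether that flatters the vaccine depends on which direction is adverse for the parameter.

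**5. How many subjects?** A masked mandatory AE needs every one of these conditions:
- deferral for acute illness
- blood already taken on the ill day
- return within 7 days with no repeat
- an ill-day value of Grade 2 or 3
- a recovered value that would have been Grade 0 or 1
- the same parameter at Grade 2 or 3 on Day 28, and no higher than on the ill day

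The expected count is 1375 times the product of these successive probabilities. The documents give 1375 and none of the probabilities, so no count can be computed.

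**The case against.** The strongest reply is that the normal sequence prevents the problem. An ill or febrile subject is picked up by the 6.1.1 examination and meets exclusion 9, so blood under 6.1.2 is not reached. That stands as a limit on numbers: the exposed group is subjects bled out of order, or found ill only after the draw. It does not remove the inconsistency, because the waiver is written for a sample already taken.

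Four further points are sound:
- The waiver is permissive. It does not forbid a repeat, and a repeat would become the baseline.
- AE reporting is not closed to other values: "The investigator may also elect to report less severe abnormalities as AEs, at his/her discretion". That clause speaks of less severe abnormalities, so it does not clearly reach a Grade 2 to Grade 2 case. The general definition in Protocol 8.1 does include unfavorable biochemical change.
- Absolute results survive. Protocol 8.1.4 tabulates laboratory values by grade, and 10.4.1.1 gives means, minima and maxima at Day 28. What is lost is the mandatory AE record and the true shift.
- Illness is assessed before any injection and, by the order of the sections, before randomization. No arm should be systematically favoured.

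A reader might infer that laboratory AEs are materially under-counted, or that the change summaries are biased towards safety throughout. The documents do not support this. They give no deferral rate and no rate of Grade 2 or higher values during illness. They do not say that every deferred subject is bled while ill. The direction of the mean-change error varies by parameter.

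**Conclusion.** The concern holds in a narrow form. The waiver conflicts with the order of procedures. If an ill-day sample is taken and not repeated, SAP 12.1 makes it the laboratory baseline. A Grade 2 or 3 ill-day value then removes the mandatory AE status of a Day 28 value of Grade 2 or 3 that is no higher, and the Day 28 change summaries use an unrepresentative reference.

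The number affected is not computable from the documents. It is probably very small, since all the conditions in step 5 must coincide. It is not expected to differ by arm. Because the safety analysis is descriptive by arm, however, equal masking across arms would not restore any AE missing from an arm's own rate. The enumeration rests on laboratory grades running from 0 to 3.

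This is a minor improvement, worth making because it is cheap, touches a component of the primary safety endpoint and settles a real inconsistency. It is not evidence that the trial's safety conclusions would change.

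**What to change.** 1. In Protocol 6.1.1 and the synopsis screening note, strike clinical laboratory testing from the waiver, so that both agree with exclusion 9 and the order in 6.1.2.
2. In SAP 12.1, add that the safety laboratory baseline is the pre-injection sample from the day of injection, as the section already says for immunogenicity.
3. Where only an ill-day sample exists, keep the subject and flag the baseline in the Day 28 grade-change table.

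The cost is two wording edits, one SAP sentence and a table flag. If the draw waits for the injection visit, no extra blood is taken. Otherwise it is at most one repeat 10 mL draw in the few subjects already bled while ill. No subject is lost from analysis.

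The serology half of the waiver also disagrees with the immunogenicity rule in SAP 12.1. That is a separate matter, but the passages should be reconciled in the same edit.
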